2. CHARACTERISTICS OF STUDY POPULATION

2.1 Subject Characteristics

Asthma and its morbidity disproportionately affect minority children of low-income families in inner cities, where asthma severity has increased and poses serious challenges to achieving adequate asthma control.⁵ Disparate burdens of asthma and its adverse outcomes among minority children have been consistently documented in the past 20 years.^{4, 23-25} In 2010, asthma prevalence in black children under 18 years was twice that of white youths; children in families below the poverty threshold as defined by the US Census Bureau were 1.5 times more likely to report current asthma than those in families at or above 200% of the poverty line.² Compared with white youth, black inner-city children are 4 and 3 times more likely to have asthma-related ED visits and hospitalizations respectively.⁴ The three cities where the study will take place, Buffalo, NY; Baltimore MD; Memphis TN demonstrate high rates of pediatric asthma, high health care utilization and high morbidity and mortality rates, thus this study will take place in these cities that are most likely to benefit from a proposed intervention.

a) Number of Subjects:

A total of 378 adolescents (12-17 years) and 42 adolescent peer leaders (16-20 years) will be recruited for this study. The sample size (N=378) is based on the power analysis using a novel method developed by Roy et al.²⁶ for a 3-level hierarchical longitudinal design based on the program "RMASS." This method has the advantage of incorporating three levels from the sites and repeated-measures from each subject with random-effects of the time trends at both the subject- and site-level, which are assumed to be equivalent in terms of sampling proportions, number of groups and differential attrition rates over time. In this proposed study, quality of life, the primary outcome, was used to estimate the sample size. Using data from the previous study,²⁷ the longitudinal trajectories of quality of life and its treatment-by-time interactions based on subject-level randomization were modeled: the estimated treatment*time interaction coefficient was 0.6 units, estimated SDs for error was 15, and the random-slope was 1.76. These estimated values with a Type-I error rate (alpha) of .05 yielded a total sample size of 276 that would detect a

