time trend over eight time points (T1-T8) between groups with a power of .80. This sample size was estimated on the assumption that the analyses use multi-site hierarchical 3-level linear mixed-effects models. In the earlier study, the attrition rate of the inner-city subsample (n=55) was 27% including those who failed to attend the camp program (n=13, 23%) and those lost to follow-up (n=2, 4%). To compensate for a possible attrition rate of 27%, the total sample size was increased to 378 (126 for each site; 63 each of two groups).

b) Gender and Age of Subjects:

Recruitment will not be limited on gender. Based on epidemiological data, we will focus on adolescents from 12-17 years of age for campers and 16-20 years of age for peer leaders.

Participants will be stratified by gender and age (younger 12-14 years, older 15-17 years), which emerged as influential covariates in the PI's earlier study. Within each of four blocks generated by each combination of these two covariates, each subject will be randomly assigned to either group using a computer-generated randomization table. Stratified randomization will ensure a similar number of subjects representing each block in the two treatment groups, balancing the influence of age and gender. Stratified randomization will be done separately for each site, and centrally coordinated and managed. Within the treatment group, participants will be assigned to subgroups based on their age [younger (12-14 years) and older groups (15-17)] to allow the study team to adjust the levels of difficulty/complexity of program content delivered at the camp. In doing so, we will attempt to enhance participants' understanding of the information covered in the program. In the previous study, we found no differences in study outcomes or camp satisfaction between gender-matched groups and co-ed groups, so subgroups will be gender-mixed.

c) Racial and Ethnic Origin:

Enrollment of participants will not be restricted to any racial or ethnic groups. By recruiting participants from three cities with high prevalence and incidence of pediatric asthma, (again based on epidemiological data) we anticipate the sample demographic to have a higher proportion of minority populations representative of the neighborhoods targeted (Buffalo, Baltimore and Memphis.)

d) Vulnerable Subjects:

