		Cognitive factors				Self-management				Asthma control					
	PAQL	AA	AT	AS	AOE	ASM	AD-S	AD-O	FEF	ACT	AEC	FEV1	SD	PFS	
T1	✓	✓	✓	✓	✓	✓	✓	✓	✓	✓	✓	✓	✓	✓	✓
T2	✓	✓	✓	✓	✓	✓	✓	✓	✓	✓	✓	✓	✓	✓	
T3	✓	✓	✓	✓	✓	✓	✓	✓	✓	✓	✓	✓	✓	✓	
T4	✓	✓	✓	✓	✓	✓	✓	✓	✓	✓	✓	✓	✓	✓	
T5	✓	✓	✓	✓	✓	✓	✓	✓	✓	✓	✓	✓	✓	✓	
T6	✓	✓	✓	✓	✓	✓	✓	✓	✓	✓	✓	✓	✓	✓	
T7	✓	✓	✓	✓	✓	✓	✓	✓	✓	✓	✓	✓	✓	✓	
T8	✓	✓	✓	✓	✓	✓	✓	✓	✓	✓	✓	✓	✓	✓	

Measures for Cost-Effective Analysis:

Health care utilization and costs associated with asthma will be assessed by (1) Medicaid claims, and (2) medical record reviews. We expect that a majority of participants will be enrolled in Medicaid as 90-95% of inner-city children/adolescents were in previous studies conducted in Rochester, Baltimore and Memphis. The Medicaid claims (to be purchased from the Centers for Medicaid & Medicare Services [CMS]) will provide the best source of data for Medicaid-covered services including office visits, ED visits, inpatient care, and prescribed medications. The Medicaid administrative data contain detailed individual-level information on treatment and procedure codes (ICD-9-CM or CPT codes), service dates and expenditures. For adolescents whose services are not available from CMS data, detailed data on service use and prescribed medications related to asthma will be collected through medical records from PCPs; HIPAA authorization will be obtained from parents. In all sites, medical record review was approved by supporting practices for participants lacking CMS data. In both cases, data will be collected between 3 months before enrollment and 3 months after completion of the 15-month follow-up. At each time point, teens and parents will report the number of missed school days due to asthma and the number of hours missed from parents' gainful employment due to the teen's asthma in

the past 3 months.

Measures of Program Evaluation.

(a) Camp Program Evaluation (CPE:7 items) will be administered at the camp to assess the campers' perception about and overall satisfaction with the program.

(b) Overall Program Evaluation (OPE: 6 items) will be completed at 15-months follow-up to assess participants' overall perceptions about the study. Each item will be examined individually.

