Aim 5: The costs of services received during visits to a physician's office, outpatient department, or ED will be estimated by taking the global relative value unit for each service CPT (Current Procedural Terminology) code multiplied by a standard conversion factor.⁶¹ Hospital charges will be converted to costs using department-specific cost-to-charge ratio.⁶² Medications and dosages prescribed will be captured; standard wholesale unit cost from the Pharmaceutical Red Book⁶³ will be used to estimate medication costs. To calculate lost productivity costs of a family with a sick teen, we will estimate total lost income related to each participant by multiplying total number of work hours missed by a parent's hourly wage. Program costs will be estimated from the actual time peer and adult leaders spent in carrying out the program multiplied by hourly earnings, costs of equipment/ supplies, and overhead costs; program time will not include staff time for research-related tasks. We will estimate the average program cost per participant by study group, and include this estimate as one component of direct healthcare costs. The

medical or general Consumer Price Index⁶⁴ will be used to inflation-adjust costs to current year prices.⁶⁴ For each teen at each time-point, we will calculate total direct costs, direct costs by major category (office visit, hospitalization), indirect lost-productivity costs, and total direct and indirect costs. For withdrawals from follow-up, we will impute missing utilization and cost data assuming a linear trend in use and cost given prior experiences, where we will estimate weighted least square regression on log-transformed cost and obtain smearing-retransformed predictions.⁶⁵ For PLASMA and control groups separately, we will calculate the cost difference between each time point and baseline for each teen, assuming (s)he received “standard care” before treatment. Cost differences for each group will be modeled against follow-up points and individual covariates to estimate the independent impacts of each program on costs relative to standard care.

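### Aim 5 fills in withdrawn teens' costs with one log-cost prediction that has no rule for zero costs and carries no imputation uncertainty, without saying that available claims are used first

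*Combined protocol and SAP*

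**What the plan says.** Section 10.1, Aim 5, sets its own rule for teens who leave follow-up: "we will impute missing utilization and cost data assuming a linear trend in use and cost given prior experiences". The means is to estimate "weighted least square regression on log-transformed cost and obtain smearing-retransformed predictions". No step for zero costs is named (two-part model, added constant or otherwise), and there are no repeated draws and no sensitivity analysis for costs.

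Costs are computed for each teen at each assessment: direct costs in total and by type of service (hospitalization is one example), lost productivity, and the sum. Direct costs include medication and an average program cost per participant. Changes from baseline are then modeled within each group.

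Four other places bear on this rule:

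- The opening of Section 10.1 offers maximum likelihood and multiple imputation as examples of how missing data in general will be handled.
- Section 4.1 (Measures for Cost-Effective Analysis) takes use and cost from Medicaid claims, or from medical records for teens without claims. The window runs from 3 months before enrollment to 3 months after the 15-month follow-up. It also states: "We expect that a majority of participants will be enrolled in Medicaid as 90-95% of inner-city children/adolescents were in previous studies". Missed work hours are self-reported.
- Section 5 withdraws camp no-shows, teens who miss three or more consecutive assessments, and those who become pregnant or incarcerated.
- Sections 7 and 8 destroy all data of anyone who asks to withdraw.

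**The concern.** The logarithm of zero is undefined. Most assessments are about three months apart, so hospitalization and lost-work costs will be zero in many cells. The analyst must drop the zeros, add a constant or change the model, and the imputed means depend on that choice.

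The rule also treats a predicted value as if it had been observed. Standard errors for cost differences and cost-effectiveness ratios will be too small, and the Aim 5 hypothesis (costs lower than control, or cost neutral) would be judged against intervals that are too narrow.

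Finally, a teen who stops attending may still have claims or a medical chart. Extrapolating that teen's direct costs would replace obtainable data with a model.

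**Working it through.** **1. Expected withdrawals.** The plan gives no figure for the cost imputation itself, so its scale comes from the attrition allowance in Section 2.1: "To compensate for a possible attrition rate of 27%, the total sample size was increased to 378". Check: 276 / (1 − 0.27) = 378.08, which matches 378. Expected withdrawals are 378 − 276 = 102, or 27%. I take the 276 as stated; nothing below depends on how it was derived. In the earlier inner-city subsample, all 15 losses out of 55 were camp no-shows (13) or lost to follow-up (2).

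**2. Zeros dropped.** With a share p0 of zeros, a model fitted to positive costs predicts the mean among users, which is 1/(1 − p0) times the overall mean. The documents give no p0; these values are assumed.

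| p0 | Imputed mean / true mean | Arm mean / true mean, f = 0.27 imputed |
|---|---|---|
| 10% | 1.11 | 1.03 |
| 30% | 1.43 | 1.12 |
| 50% | 2.00 | 1.27 |

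The last column is 1 + f × [1/(1 − p0) − 1], assuming that withdrawn and retained teens have the same true mean.

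**3. Constant added.** This was checked by simulation. Positive costs were log-normal (log mean 5.5, log SD 1, both assumed), with 20,000 costs per period. A linear trend in log cost was fitted to periods 1–4, and period 8 was predicted with smearing. Entries are predicted mean / true mean.

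| Handling of zeros | Zero share steady at 20% | Zero share rising from 20% to 40% |
|---|---|---|
| Dropped | 1.21 | 1.70 |
| Add 0.01 | 1.00 | 0.29 |
| Add 1 | 0.99 | 0.56 |
| Add 10 | 0.98 | 0.76 |

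The formula in step 2 gives 1.25 and 1.67 for the first row, close to the simulated values. A constant does little harm while the zero share is steady. When the share changes, the answer depends heavily on the constant.

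**4. Uncertainty.** Let a fraction f be filled with regression predictions that explain R² of the variance. In units of σ²/N, the naive variance of the mean is (1 − f) + f·R², and the correct one is R² + (1 − R²)/(1 − f). With f = 0.27, the ratio of naive to correct SE is:

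- R² = 0: 1 − 0.27 = 0.73
- R² = 0.3: √(0.811/1.259) = 0.80
- R² = 0.5: √(0.865/1.185) = 0.85

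On a normal approximation, a nominal 95% interval then reaches 1.96 × 0.73 = 1.43 to 1.96 × 0.854 = 1.67 correct SEs. Coverage is about 85% to 91%, before any bias.

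**5. How much imputation claims could avoid (direct costs only).** Let m be Medicaid coverage among withdrawn teens, assumed equal to that of the sample.

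- m = 0.90: 91.8 of 102 could have claims, leaving 10.2, or 10.2/378 = 2.7%.
- m = 0.95: 96.9 of 102 could have claims, leaving 5.1, or 5.1/378 = 1.4%.

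Both are before chart review. At these fractions the SE ratio in step 4 is 0.97 to 0.99. The plan itself commits only to a majority; at m = 0.50 the remainder would be 0.27 × 0.50 = 13.5%.

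If a share r of withdrawals is by request, with data destroyed, the share with claims is m(1 − r): 81–86% at r = 10%, 68–71% at 25% and 45–48% at 50%. Claims cover most withdrawn teens while r is below 1 − 0.5/m, that is 44–47%. The documents give no r.

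**6. Functional form.** The text assumes a linear trend in cost but fits log cost. A line in log cost is an exponential curve in cost, so the two statements do not describe the same model. For a camp no-show, only T1 and T2 precede the camp, so T3–T8 would be extrapolated from pre-camp experience.

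**The case against.** The strongest reply is that the plan may already intend the right thing. It imputes only missing data, and costs obtained from claims or charts are not missing. The opening of Section 10.1 promises distribution checks to guide the choice of model, and it mentions multiple imputation. Aim 5 also cites a paper comparing models of medical-care demand, which might contain a step for zeros.

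Part of this stands. Claims may well be meant to come first, and the fault there is an unstated order of precedence. The cited paper is not available here, so what it implies is unknown. But Aim 5 states a specific rule of its own, and a general list of example methods elsewhere does not replace it. Followed as written, the rule is undefined at zero and passes no imputation variance forward.

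A reader might infer more than the documents support:

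- **That imputed costs are biased upward.** This holds if zeros are dropped. Step 3 shows almost no bias, or downward bias, if a constant is added.
- **That the inflation could reach fivefold.** That needs 80% zeros, 1/(1 − 0.8). It could fit a sparse category such as hospitalization. Total direct cost includes medication and program costs, and eligibility requires persistent asthma and recent service use, so it will seldom be zero.
- **That a quarter of participants are affected.** This is the size only if claims are not used for direct costs.
- **That most of the imputation is unnecessary.** Lost work hours are self-reported and never appear in claims, so lost productivity and the combined total still need imputation. Claims for withdrawn teens may be obtainable, but the documents do not say that authorization continues after withdrawal.

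**Conclusion.** The point holds for the economic aim. The rule cannot be applied to zero-cost cells and understates uncertainty. The direction of bias is undetermined until the handling of zeros is fixed, and no effect on the between-arm difference can be computed because withdrawal by arm is not given.

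The standard-error ratio of 0.73–0.85 applies where the full 27% is imputed, as it could be for lost productivity, or for direct costs if claims are not used. It assumes R² between 0 and 0.5. With claims used first, imputed direct costs fall to about 1.4–2.7% of participants and the distortion nearly disappears. That rests on 90–95% coverage among withdrawn teens, continuing authorization and few requests to withdraw.

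There is a further conflict: teens whose data are destroyed on request leave no prior experience from which to impute. The primary outcome, quality of life, is not affected.

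**What to change.** 1. State that, for teens withdrawn by rule or lost to follow-up who have not asked to withdraw, direct costs come from CMS claims and medical records over the full Section 4.1 window, where authorization permits.
2. For direct costs still missing and for self-reported lost productivity, replace the single log-cost fill-in with multiple imputation by arm under a model that admits zeros. A two-part model is one suitable choice: any cost, then a log-link gamma model or log cost among users. Carry the imputation variance into the intervals for cost differences and cost-effectiveness ratios.
3. Reconcile Aim 5 with the general missing-data paragraph of Section 10.1, and state one form for the time trend. Reconcile it also with Sections 7 and 8, by saying how teens whose data are destroyed enter the cost analysis, if at all.

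The cost is SAP wording, modest programming, and a check that the HIPAA authorization covers teens who stop attending. Sample size and study visits do not change.

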Hypothesis: We hypothesize that: relative to the control group, the PLASMA group will report greater improvement over time in (H1) quality of life (primary outcome), and (H2) asthma knowledge, attitudes, outcome expectations, self-efficacy, self-management skills, and asthma control, FEV1 (exploratory outcomes). (H3) The post-PLASMA scores on outcome measures will be higher than pre-program scores from both treatment groups.

- 2) To examine the mediating effects of the secondary outcomes (knowledge, attitudes, outcome expectations, self-efficacy, self-management skills, asthma control, and FEV1) on the primary outcome (quality of life) of the intervention.
- 3) To examine the moderating effects of personal factors (e.g., age, sex, family support) on primary and secondary outcomes of the intervention.
- 4) To evaluate the effects of PLASMA on primary and exploratory outcomes in peer leaders (16-20 years).

Hypothesis: We hypothesize that the peer leaders (n=42) will report significant improvement in quality of life (primary outcome) and secondary outcomes (knowledge, attitudes, outcome expectations, self-efficacy, self-management skills, asthma control and FEV1) over the course of 15 months.

- 5) To determine the economic impact of the intervention. This aim will be accomplished by (5a) measuring the direct healthcare costs and total costs of the PLASMA program, as compared with the control group; (5b) performing net cost analyses for each type of costs; and (5c) estimating cost-effectiveness ratios of the PLASMA group compared with the control.

Hypothesis: We hypothesize that the direct and overall costs per participant in the PLASMA group will be less than costs per participant in the control group, or cost neutral.

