10. DATA ANALYSIS AND DATA MONITORING

10.1 Planned Statistical Analysis: Analyses will be performed using SAS, and R⁵⁶ will be used as analysis software to ensure the validity and reproducibility of the results. We will perform descriptive statistics on each outcome measure to look for abnormality and outliers. If a measure is not normally distributed, transformation will be applied. We will identify and investigate outliers for sources of errors, and conduct preliminary analyses on data distribution and bivariate correlations to determine the appropriate statistical model as well as the final interpretation of the results. We will investigate missing data with pattern analysis for data missing completely at random (MCAR), missing at random (MAR) or missing not at random (MNAR), and use statistical methods appropriate for each type such as maximum likelihood and multiple imputation to impute missing values so full analysis can be performed with sensitivity. We will compute Cronbach's alphas for psychometric measures, and assess construct validity using exploratory or confirmatory factor analysis when appropriate. The PLASMA and control groups will be compared on baseline data to determine any systematic differences; if any are found, analyses will include the variables as covariates in the model to adjust for the imbalances.

Aim 1: A multi-site hierarchical three-level linear mixed-effects model,^{26, 56, 57} where level 1 represents repeated measures, level 2 = subject, and level 3 = site, will be used to analyze treatment differences and treatment-by-time interaction described in the following notation by Hedeker and Gibbons.⁵⁷

Aim 2: The mediating effects will be examined mainly using the mediation methods of Baron & Kenny.⁵⁸ When found significant, a multiple mediation analysis⁵⁹ procedure will be used to further determine whether the effect of PLASMA on quality of life is mediated jointly by multiple exploratory outcomes.

Aim 3: Moderating effects will be examined by multiple linear models and generalized linear models described in Berridge and Crouchley⁵⁶ or Chen and Peace⁶⁰ along with the above multi-site hierarchical three-level linear mixed-effects models.

Aim 4: This aim will be tested by applying the multi-site hierarchical two-level linear mixed-effects models described in the analysis for Aim 1, with level 1 representing longitudinal measurements and level 2 sites.

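### Aim 5 plans a PLASMA-versus-control cost comparison, but the only cost model specified is a before-after model for each arm, with no between-arm estimator or interval

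*Combined protocol and SAP*

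**What the plan says.** Section 1 sets Aim 5 in three parts: measuring direct and total costs of PLASMA against the control group (5a), "performing net cost analyses for each type of costs" (5b), and "estimating cost-effectiveness ratios of the PLASMA group compared with the control" (5c). The hypothesis is that cost per participant is lower under PLASMA than under control, or cost neutral.

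Section 10.1 (Aim 5) covers unit costs, inflation adjustment and imputation for withdrawals, then gives one modelling step. The outcome is set first: "For PLASMA and control groups separately, we will calculate the cost difference between each time point and baseline for each teen". The reference period rests on a stated assumption, worded as "assuming (s)he received “standard care” before treatment". On the model, the plan says: "Cost differences for each group will be modeled against follow-up points and individual covariates". The declared purpose of that model is "to estimate the independent impacts of each program on costs relative to standard care". On the cost of the programs themselves: "We will estimate the average program cost per participant by study group, and include this estimate as one component of direct healthcare costs".

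For comparison, Aim 1 in the same section has a three-level mixed model that "will be used to analyze treatment differences and treatment-by-time interaction". Aims 3 and 4 refer back to that model. Aim 5 does not.

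**The concern.** The question is between arms and the model is within arms. Cost after the camp may differ from cost at baseline for reasons unrelated to either program. The documents suggest several:

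- season and ageing over a 21-month study;
- possible regression to the mean, since Section 2.2 requires asthma-related service use in the 12 months before recruitment (although preventive use also qualifies);
- reports and alerts to primary care providers, sent for both groups (Section 4.1).

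A one-arm model credits all of this to the program. Section 7.2 directs the economic results to policy makers who might adopt the program as standard care, so before-after change reported as program impact could mislead the readers the aim is meant to serve.

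The trial already has the remedy. Teens are randomized, and Section 4.1 holds the control camp within 2 weeks of the peer-led camp so that outside events affect both arms alike. That protection belongs to the between-arm contrast.

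**Working it through.** There is no figure to reproduce. The documents give no standard deviation, power, sample size or margin for costs; the alpha of .05 and the 276 in Section 2.1 belong to quality of life. The check is therefore a comparison of texts, followed by two short calculations.

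**1. Aim against analysis**

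| Item | Section 1, Aim 5 | Section 10.1, Aim 5 |
|---|---|---|
| Comparator | control arm | each teen's own pre-treatment period |
| Quantity | cost against control (5a), net cost (5b), ratio against control (5c) | change from baseline, for each group |
| Arm or arm-by-time term | needed by the question | none named |
| Standard error or interval | not given | not given |
| Effect measure for the ratio | not named | not named |
| 'Net cost', 'cost neutral' | used, not defined | not mentioned |

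**2. What each estimate contains.** Let s be the cost change that both arms would show anyway, and let P and C be the program effects on cost in the PLASMA and control arms.

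- Within-arm change, PLASMA: P + s.
- Within-arm change, control: C + s.
- Difference: (P + s) − (C + s) = P − C.

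The specified model estimates the first two lines and labels them program impact. Only the third line is free of s, and it is the quantity that 5a, 5c and the hypothesis need.

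**3. Why two within-arm results cannot replace the contrast.** Suppose both arms have the same true change, so P − C = 0, and each arm's test independently has power p. The chance that exactly one arm is significant is 2p(1 − p), and that only PLASMA is significant is p(1 − p).

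| p | exactly one arm significant | only PLASMA significant |
|---|---|---|
| 0.3 | 2 × 0.3 × 0.7 = 0.42 | 0.21 |
| 0.5 | 2 × 0.5 × 0.5 = 0.50 | 0.25 |
| 0.8 | 2 × 0.8 × 0.2 = 0.32 | 0.16 |

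The values of p are assumed, because the documents give no power for costs.

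**4. Precision.** With equal variances and equal arm sizes, the standard error of the difference is √2 = 1.41 times that of one arm's change. A reader who sees only the within-arm intervals would overrate how precisely the comparison is known.

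**The case against.** **The comparison is already planned.** Parts 5a to 5c name it, and the two arm estimates can be subtracted to give a difference-in-differences in which common change cancels. This stands in part. A reader might infer that the Aim 5 hypothesis would go untested; the documents do not support that, because Section 1 commits the team to the comparison. What is missing is the estimator, its uncertainty and the calculation of the ratio, while the one model that is written down names a different comparator.

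**'Separately' may apply only to calculating change scores, with one joint model to follow.** That reading is possible. But the next sentence again says for each group, names standard care as comparator and lists no program contrast, so none is specified on either reading.

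**The common causes are not quantified.** True. Alerts to primary care providers are triggered by each teen's data, so they need not be equal across arms, and Section 4.1 says the reports will be considered in the analysis, without giving a method.

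**Season.** A reader might go further and count seasonal mismatch. With T1 as baseline, T4 to T8 fall 9, 12, 15, 18 and 21 months later, and only T5 (1 of 5) returns to the same time of year. That count is not firm. If baseline means all pre-treatment cost, from 3 months before enrollment to the camp at month 6, and each point looks back 3 months, then T5, T6 and T7 match (3 of 5). The 3-month look-back is stated for missed school and work, not for claims, which carry service dates. Neither count measures a bias.

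**Change against usual care matters to payers.** It does, and the control is an active camp. That is a reason to keep the before-after results as secondary, not to let them carry a causal label.

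**Conclusion.** The point holds as a mismatch between aim and analysis. Aim 5 plans a comparison with control, but Section 10.1 specifies only before-after change in each arm, calls it program impact, and gives no estimator or interval for the between-arm cost difference or ratio. This is more than missing detail, because the stated model mixes program effect with common change and does not use the randomized contrast that the design protects.

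The size and direction of any bias cannot be derived from the documents. The probabilities of 0.32 to 0.50 above illustrate, under assumed power and independence, why two within-arm results are not a comparison; they do not forecast this trial. The conclusion rests on reading the Aim 5 text as written, with the Aim 1 model not extended to costs. It concerns Aim 5 only and should be settled before cost data are analysed.

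**What to change.** Amend the Aim 5 text in Section 10.1 as follows.

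- **Model.** Test the hypothesis in a single model including both arms, with an arm term or arm-by-time terms, adjusted for baseline cost, site, sex and age group.
- **Population.** Include all randomized teens as assigned, as far as their claims, records or imputed costs allow. This includes those withdrawn under Section 5 for missing camp. The earlier inner-city subsample lost 23% that way (Section 2.1); the same rate here would be 0.23 × 378, about 87 teens.
- **Window.** Use the full period for which the plan collects cost data, to 3 months after the 15-month follow-up.
- **Report.** Give the adjusted PLASMA-minus-control cost difference with a confidence interval from a method suited to skewed costs, for example a bootstrap. Program cost enters as one average per arm, so it shifts the difference by a fixed amount; show that part separately.
- **Ratio (5c).** Base it on that cost difference and the between-arm quality-of-life difference, and report its uncertainty.
- **'Cost neutral'.** Judge it from the interval, not from a non-significant test or from comparing two within-arm results. The documents define no margin, so say in advance how the interval will be read.
- **Within-arm changes.** Keep them as secondary results, labelled as before-after change and not as causal program impact.

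The cost is revised wording and modest extra programming, with no new data. The result may be less favourable to the program, and because control is an active camp, the contrast does not estimate cost against usual care.
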